9. STATISTICAL CONSIDERATIONS AND DATA ANALYSIS

9.1 Study Design and Sample Size Determinations

9.1.1 Dose Escalation

The SL-172154 dose escalation will utilize an mTPI-2 design [Guo, 2017] with a target DLT rate of 30% for the MTD.

The mTPI-2 design employs a simple Beta-Binomial Bayesian model with decision rules based on the unit probability mass from the posterior probability of DLT rate. With the target DLT rate of 30%, the posterior probability of DLT rate unit interval (0, 1) is divided into subintervals with equal length of 0.1 that correspond to different dose escalation decisions: subinterval of (0.25, 0.35) is to stay at the current dose, subintervals below 0.25 is to escalate to next higher dose, and subinterval above 0.35 is to de-escalate to the next lower dose. Subjects will be enrolled in cohorts of approximately 3 subjects during the dose escalation. After each cohort of approximately 3 subjects, the posterior unit probability for subintervals will be calculated based on a noninformative prior distribution for the DLT rate (Beta (1,1)) and the total number of subjects with DLTs and DLT-evaluable subjects for the current dose. A dose escalation/stay/de-escalation decision that corresponds to the subinterval with the highest unit probability mass will be selected. A minimum of 3 DLT-evaluable subjects will be enrolled to a dose level and evaluated for DLT before a dose escalation/stay/de-escalation decision can be made unless unacceptable toxicity is observed prior to the enrollment of 3 subjects e.g., two subjects experience DLT before the third subject enrolls. A dose level will be considered unsafe, with unacceptable toxicity and no additional subjects enrolled at that dose level and above, if it has an estimated 95% or more probability of exceeding the target DLT rate of 30%. The maximum number of subjects evaluated for DLT for each dose level will be 12 subjects (about 4 cohorts of 3 subjects) if the dose escalation decision is to stay at the current dose from the first 3 cohorts. Based on the above design, the dose escalation decision rules for each dose level are:

- Dose escalate if the observed DLT rate < 25%;
- Stay at the current dose if the observed DLT rate between 25%-33%;
- Dose de-escalate if the observed DLT rate > 33%;

See [Table 12](#) for dose escalation decision rules based on the total number of subjects evaluable for DLT and the number of DLTs observed.

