9.2.4 Safety Analyses

The safety evaluation for each combination regimen will be based on the All-Treated Population and the DLT evaluation will be based on the DLT-evaluable population.

DLTs will be summarized by dose level/regimen for combination dose escalation cohorts. Frequency tables by dose levels will be used to describe safety and tolerability parameters such as: AEs, SAEs, fatal AEs and AEs leading to discontinuation of SL-172154, PLD or MIRV. Changes in toxicity grade for safety assessments (e.g., laboratory parameters, etc.) will also be summarized. Figures may also be presented where appropriate. AEs will be mapped to a Medical Dictionary for Regulatory Activities (MedDRA) preferred term and system organ classification. Concomitant medications will be coded using the World Health Organization Drug Dictionary. All toxicities except CRS and ocular AEs will be graded according to the NCI CTCAE v5.0. CRS will be graded per the ASTCT Consensus Grading Criteria for CRS (described in

Section 3.7.1.2); ocular AEs for the MIRV cohort will be graded per the tables provided in Appendix Section 16.6.

Maximum Tolerated Dose:

The MTD will be estimated using isotonic regression (based on the DLTs observed in DLT-evaluable subjects). Specifically, the MTD is the dose for which the isotonic estimate of the DLT rate is closest to the target DLT rate of 30% among all dose with the isotonic estimate of DLT rate $\geq 25\%$. If two or more doses tie for the smallest difference, the following rules will be performed:

- If the estimated DLT rate $< 30\%$ for all doses, then select the higher dose among the tied doses;
- If the estimated DLT rate for the tied doses are a combination of $< 30\%$ and $> 30\%$ for all doses, then select the higher dose among the tied doses;
- If the estimated DLT rate $> 30\%$ for all doses, then select the lower dose among the tied doses;

A Maximum Administered Dose (MAD) will be reported if the isotonic estimate of DLT rate is less than 25% for all dose levels. Otherwise, an MTD will be reported.

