8.2 Maximum Tolerated Dose Evaluation

The MTD evaluation will be based on the DLT Evaluable Population. The number and percentage of subjects with DLT will be presented by dose level for the dose escalation cohorts. The MTD level will be indicated in the summary.

The MTD will be estimated using isotonic regression (based on the DLTs observed in the DLT evaluable subjects). A MAD will be reported if the DLT rate never reaches $\geq 25\%$. Otherwise, an MTD will be reported. Isotonic regression is a way to estimate the MTD under the assumption that toxicity increases with dose. When using isotonic regression, the first step is to identify the doses where the dose-toxicity monotonicity assumption is violated. The DLT estimate is then adjusted for the violators such that the final estimate of the DLT rate increase with the dose. The target DLT rate is then used to select the MTD. For example, suppose that when the trial is completed, the observed DLT rates [<# subjects who experienced DLT]/[# evaluable subjects] at four dose levels are (0/3, 1/3, 0/3, 4/15). In this example the observed DLT rate at Dose Level 2 (i.e., 1/3=33%) is higher than the observed DLT rate at Dose Level 3 (i.e., 0/3=0%). To adjust for this violation, the DLT estimates are replaced with their average, i.e., $(1/3+0/3)/2=1/6$, resulting in the isotonic regression DLT estimates $(0/3, 1/6, 1/6, 4/15) = (0\%, 16.7\%, 16.7\%, 26.7\%)$, which monotonically increases with the dose level. Based on this isotonic estimate, assuming that the trial goal is to find the dose with the DLT rate of 30%, Dose Level 4 will be selected as the MTD. If there are no violators of the dose-toxicity monotonicity assumption, isotonic regression directly uses the observed DLT rates as the final estimates for MTD selection.

In the case of dose levels with estimated toxicity of equal distance (tied dose levels) from the target toxicity of 30%, the following approach will be used: among all tied dose levels the highest dose level with target toxicity $\leq 30\%$ will be selected, unless all tied dose levels have estimated toxicity $> 30\%$, in which case the lowest dose level will be selected.

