11. CHANGE FROM PROTOCOL-SPECIFIED ANALYSES

There are no changes from the protocol-specified analyses.

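### Protocol 9.2.4 and SAP 8.2 give different MTD rules (25% floor, tie-break, MAD wording), so the same DLT data can name a different MTD, mainly because the SAP omits the floor.

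*Protocol*

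**What the plan says.** Both documents estimate the MTD by isotonic regression on DLT-evaluable subjects, with a 30% target. They differ on three details.

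- **Candidate doses.** In Protocol 9.2.4 "the MTD is the dose for which the isotonic estimate of the DLT rate is closest to the target DLT rate of 30"%, but the search is restricted: "among all dose with the isotonic estimate of DLT rate" of 25% or more. SAP 8.2 says only that the target rate is used to select the MTD. Its tie paragraph speaks of equal distance from 30%, which implies nearest to 30%. It gives no floor.
- **Ties.** In Protocol 9.2.4, where the tied estimates "are a combination of $< 30\%$ and $> 30\%$ for all doses, then select the higher dose among the tied doses". In SAP 8.2, "among all tied dose levels the highest dose level with target toxicity" of at most 30% is chosen, and the lowest tied dose is taken only if all of them exceed 30%.
- **MAD instead of MTD.** In the protocol a MAD "will be reported if the isotonic estimate of DLT rate is less than 25% for all dose levels". In the SAP, "A MAD will be reported if the DLT rate never reaches" 25%, without saying whether the rate is observed or isotonic, interim or final.

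SAP Section 11 states: "There are no changes from the protocol-specified analyses". Protocol 9.2 requires deviations from the protocol's analysis to be documented in the SAP.

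**The concern.** The MTD or MAD in each regimen is listed as a primary outcome measure (Protocol Section 2). The tables will be programmed from the SAP, while readers will take the protocol as the definition. If the two rules pick different doses from the same DLT counts, the reported MTD depends on which document was coded, and the SAP's statement of no change gives no warning of it.

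**Working it through.** **Inputs.** Target DLT rate 30%; protocol floor 25%; at most 12 DLT-evaluable subjects per dose level (Protocol 9.1.1); levels of 1.0, 3.0 and 6.0 mg/kg starting at 3.0; escalation decisions from Protocol Table 12. Isotonic estimates come from pooling adjacent violators.

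**The SAP's own example.** Observed 0/3, 1/3, 0/3, 4/15. Levels 2 and 3 violate monotonicity and are averaged: (1/3 + 0/3)/2 = 1/6. The estimates are 0%, 16.7%, 16.7% and 26.7%, and Dose Level 4 is selected. This reproduces. Both documents' rules give the same answer here, so the example does not expose the difference.

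**1. Candidate set.** Take 1/6 at 3.0 mg/kg and 3/6 at 6.0 mg/kg. Table 12 can produce this with cohorts of 3, using the 12 escalation subjects planned for a regimen. The estimates are 16.7% and 50%.
- Distances from 30%: 30 − 16.7 = 13.3 points and 50 − 30 = 20 points.
- SAP, no floor: 3.0 mg/kg is nearer and is the MTD.
- Protocol: 16.7% is below 25%, so 6.0 mg/kg is the only candidate and is the MTD.

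The pair 2/10 and 4/10 (20% and 40%), or 1/5 and 2/5, gives the same split. In the SAP these are ties at 10 points each, resolved to 3.0 mg/kg. In the protocol there is no tie, because 20% is under the floor, and 6.0 mg/kg is selected.

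All data states reachable under Table 12 with cohorts of 3 were enumerated, allowing a stop at any point. The two documents name different MTDs in 426 of about 2,030 (421 if violators are averaged without weighting by sample size). The denominator depends on how a de-escalation from the lowest level is handled; the 426 does not. In 422 of the 426 the cause is the floor with no tie. The other 4 are ties in the SAP only, because the lower dose is under the protocol's floor. If the floor is added to the SAP, the tie wording changes the MTD in none of these states, and in none of 50,025 states with cohorts of 2 to 4.

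A share of states is not a probability. In simulations with cohorts of 3, 12 subjects per regimen and assumed true DLT rates from 5/10/15% to 20/30/45% at the three levels, the documents named different MTDs in about 4% to 39% of runs.

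**2. Tie rule.** A protocol tie across 30% needs one estimate from 25% to under 30% and its mirror image above 30%. With at most 12 subjects, the observed rates in the lower band are 25% (1/4, 2/8, 3/12), 27.3% (3/11) and 28.6% (2/7). Their mirrors are 35%, 32.7% and 31.4%, and no fraction with a denominator of 12 or less equals any of these. Pooling can create such a tie in a three-dose pattern such as 1/3, 3/12, 1/3 (pooled 4/15, against 1/3), but Table 12 cannot reach it.

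With more subjects the conflict is live: 4/15 = 26.7% and 4/12 = 33.3% are each 3.3 points from 30%. The protocol selects the higher dose and the SAP the lower. Protocol 9.1.4 allows added subjects and dose levels.

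**3. MAD trigger.** Three readings of the SAP's unspecified rate:
- Final isotonic estimate: identical to the protocol.
- Final observed rate: can differ in principle (1/3 then 0/3 pools to 16.7% each), but in no reachable state.
- Any interim observed rate: differs. A dose at 1/3 that ends at 1/6 has reached 25%, so the SAP would report an MTD, while the protocol reports a MAD if every final estimate is below 25%. This holds in 67 of the reachable states. In simulation it occurred in roughly 7% to 40% of escalations, a range that is conditional on this reading.

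**The case against.** Four points can be made in the plan's defence.

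First, SAP 8.2 may be meant only as a summary, with the protocol's floor carried over because Section 11 declares no change. That may be the intention, but SAP 8.2 describes selection step by step with a worked example and never mentions a floor.

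Second, a reader might infer that the contradictory tie rules are what drive the different MTDs, taking 2/10 against 4/10 as the case in point. The documents do not support that. The protocol drops the 20% dose before any tie arises, so its tie bullet is never used. Harmonising the tie sentence alone would leave that example unchanged.

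Third, a reader might infer that the MAD triggers plainly differ. In context the SAP sentence directly follows the statement that the MTD is estimated by isotonic regression, and the paragraph goes on to refer to final estimates once the trial is complete. The natural reading agrees with the protocol; what remains is loose wording.

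Fourth, the RP2D rests on the totality of safety, tolerability, PK, PD and efficacy data (Protocol 3.4; SAP 3.1.3), and escalation follows Table 12 rather than this end-of-study estimator. That stands. The discrepancy affects the reported MTD and does not by itself change the RP2D or any escalation step.

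**Conclusion.** The discrepancy is real and should be corrected. Its main source is the 25% candidate floor, present in the protocol and absent from the SAP: 426 of about 2,030 reachable states name a different MTD. This assumes cohorts of 3 and the SAP read as nearest to 30% with no floor. The tie sentences contradict each other outright, but under the protocol's floor and the 12-subject cap the contradiction has no effect in any state reachable through Table 12; it matters only with added subjects or dose levels. The MAD triggers differ in wording, and in result only if an interim observed rate is allowed to count. None of this shows that either document's dose-selection rule is the wrong one, only that the two must be reconciled.

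**What to change.** Before database lock, reconcile Protocol 9.2.4 and SAP 8.2 so that both state:

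1. one candidate set, with or without the 25% floor;
2. one rule for tied doses on both sides of 30%;
3. one MAD trigger that names the rate used, which the protocol already defines as the final isotonic estimate at every dose level.

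In the SAP tie sentence, change target toxicity to estimated toxicity, since the target is fixed at 30% and only the estimate varies by dose. Record any difference that is kept in SAP Section 11. Items 1 and 2 are the sponsor's choice; the requirement is that both documents say the same thing. The cost is a few sentences and a check that the program matches, with no effect on data collection or sample size. For data such as 1/6 and 3/6, the choice on item 1 settles which dose is reported as the MTD, so it should be made without reference to the observed DLT counts where that is still possible.

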9.2.5 Efficacy Analyses

Anti-tumor activity data will be summarized by dose level and all subjects for each combination regimen in the All Treated population and Response-Evaluable population. For the MIRV combination regimen, the anti-tumor activity will be summarized for each of the three tumor FR α expression subgroups: high (PS2+ $\geq 75\%$), medium (PS2+ $\geq 50\%$ and $< 75\%$), and low (PS2+ $\geq 25\%$ and $< 50\%$). The ORR and CBR based on investigator-assessed response per RECIST v1.1 will be estimated along with a 95% confidence interval using the exact probability method. Change from baseline sum of diameters for target lesions will be provided for each subject. DOR and TTR will be evaluated, using the Kaplan-Meier method, for the subgroup of subjects with a confirmed response. The Kaplan-Meier method will be used to estimate the PFS/OS curve and PFS/OS rate at time point of interest.

9.2.6 Pharmacokinetic Analysis

Plasma concentrations for SL-172154 will be summarized using tabular and graphical format. SL-172154 PK parameters will be derived from the plasma concentration vs. time curve (using actual dose and collection times) using Phoenix WinNonlin version 6.3 or later (Pharsight Corp.), as data permits. SL-172154 PK parameters will be summarized and analyzed using appropriate statistical methods. The relationship between PK exposure parameters and ADA, safety, efficacy, and PD endpoints may be explored, as data permit, using appropriate graphical and statistical methods.

Plasma concentrations for MIRV will also be summarized. All concentration data will be determined using validated assays.

Table 14 Serum SL-172154 PK Parameters

Parameter	Description
C_{max}	Maximum observed concentration
T_{max}	Time of maximum observed concentration
AUC_{last}	The area under the serum concentration time curve, from time 0 to the last quantifiable concentration, calculated by a combination of linear and logarithmic trapezoidal methods (Linear up/log down method).
AUC_{0-t}	The area under the serum concentration time curve, from time 0 to time=t, calculated by a combination of linear and logarithmic trapezoidal methods (Linear up/log down method).
AUC_{0-inf}	Area under the serum concentration time curve from time 0 extrapolated to infinity, calculated as $AUC_{last} + C_{last}/\text{terminal elimination rate constant } (\lambda_z)$. Reliability of AUC_{0-inf} values is contingent on the percent of the total area obtained by extrapolation: AUC_{0-inf} values with < 20% of the total area coming from C_{last}/λ_z are considered acceptable. Any exceptions to the above procedures will be clearly documented/justified in the PK report.
AUC_{tau}	The area under the serum concentration time curve, over the dosing interval following doses > first dose, calculated by a combination of linear and logarithmic trapezoidal methods (Linear up/log down method)
% AUC_{ext}	Percentage of AUC_{0-inf} due to extrapolation from T_{last} to infinity
$t_{1/2}$	Terminal elimination half-life, estimated using the equation $[\ln(2)/\lambda_z]$
CL	Clearance; calculated as Dose/ AUC_{0-inf}
V_z	Volume of distribution; calculated as Dose/ $(\lambda_z * AUC_{0-inf})$
V_{ss}	Volume of distribution at steady state

PK parameters based on the elimination phase (e.g., AUC_{0-inf} , $t_{1/2}$, CL, V_z) will be calculated and reported as data allow.

9.2.6.1 Immunogenicity Analysis

The immunogenic potential of SL-172154 will be assessed by summarizing the number/proportion of subjects with positive and negative postdose ADA titer by SL-172154 dose level. ADA titer, neutralization capacity, duration of ADA response and whether ADA are transient or persistent will be listed for each individual and summarized by SL-172154 dose level. As data permit, the effect of ADA on PK and PD parameters, safety and efficacy will be explored using appropriate graphical and statistical methods.

The immunogenic potential of MIRV will also be assessed.

9.2.7 Pharmacodynamics Analysis

The PD data analysis will be based on the PD population. PD biomarkers values will be summarized descriptively by SL-172154 dose level for each combination regimen.

10. CLINICAL MONITORING

Clinical site monitoring is conducted to ensure that the rights and well-being of human subjects are protected, that the reported trial data are accurate, complete, and verifiable, and that the conduct of the trial complies with the currently approved protocol/amendment(s), with GCP, and with applicable regulatory requirement(s).

- Monitoring for this study will be performed by Sponsor or its designees
- Details of clinical site monitoring are documented in a Clinical Monitoring Plan (CMP). The CMP describes in detail who will conduct the monitoring, at what frequency monitoring will be done, at what level of detail monitoring will be performed, and the distribution of monitoring reports.
- Independent audits will be conducted by the Sponsor or designee of the Sponsor to ensure GCP and monitoring practices are performed consistently across all participating sites and that monitors are following the CMP.

11. SOURCE DOCUMENTS AND ACCESS TO SOURCE DATA AND DOCUMENTS

11.1 Source Data

Source documents are where data are first recorded, and from which subjects' eCRF data are obtained. These include, but are not limited to, hospital records (from which medical history and previous and concurrent medication may be summarized into the eCRF), clinical and office charts, laboratory and pharmacy records, diaries, microfiches, radiographs, and correspondence.

11.2 Access to Data

The study monitor, other authorized representatives of the Sponsor, representatives of the IRB/IEC or regulatory authorities may inspect all documents and records required to be maintained by the investigator, including but not limited to, medical records (office, clinic, or hospital) and pharmacy records for the subjects in this study. The clinical study site will permit access to such records to permit study-related monitoring, audits and inspections.

The study subject's contact information will be securely stored at each clinical site for internal use during the study. At the end of the study, all records will continue to be kept in a secure location for as long a period as dictated by local IRB/IEC and Institutional regulations.

Study subject research data, which is for purposes of statistical analysis and scientific reporting, will be transmitted to and stored by the Sponsor. This will not include the subject's contact or identifying information. Rather, individual subject's and their research data will be identified by a unique study identification number. The study data entry and study management systems used by clinical sites and by Sponsor research staff will be secured and password protected. At the end of the study, all study databases will be de-identified and archived by the Sponsor.

11.3 Data Recording and Record Keeping

All trial data will be entered on electronic data entry systems that are validated and are maintained in accordance with Standard Operating Procedures. The subjects will be identified by a unique trial specific number and/or code in any database. Subject name and any other identifying detail will NOT be included in any trial data electronic file.

12. QUALITY ASSURANCE PROCEDURES

The trial will be conducted in accordance with the current approved protocol, GCP, relevant regulations and standard operating procedures. Regular monitoring will be performed according to GCP. Data will be evaluated for compliance with the protocol, GCP, and accuracy in relation to source documents. Following written standard operating procedures, the monitors will verify that the conduct of the clinical trial and data generated, are documented, and reported in compliance with the protocol, GCP and the applicable regulatory requirements.

13. ETHICS/PROTECTION OF HUMAN SUBJECTS

13.1 Ethical Standard

The investigator will ensure that this study is conducted in full conformity with Regulations for the Protection of Human Subjects of Research codified in 45 Code of Federal Regulations (CFR) Part 46, 21 CFR Part 50, 21 CFR Part 56, and/or the ICH E6 or in compliance with the Declaration of Helsinki, CIOMS, International Ethical Guidelines for Biomedical Research Involving Human Subjects (2002), or ethical policy statement specific to the country, whichever provides the most protection to human subjects.

13.2 Institutional Review Board/Independent Ethics Committee

The protocol, ICF(s), recruitment materials, and all subject materials will be submitted to the IRB/IEC for review and approval. Approval of both the protocol and the consent form must be obtained before any subject is screened and enrolled. Any amendment to the protocol will require review and approval by the IRB/IEC before the changes are implemented to the study. All changes to the consent form will be IRB/IEC approved; a determination will be made regarding whether previously consented subjects need to be re-consented.

